- ERQ13 To conduct a latent class mediation analysis to explore how the volume of violent offences is mediated by the frequency and type of substance used at 6 and 12 months.

Part of this work will be to examine the potential impact of both UK and region-specific issues that may be linked to race, ethnicity, sex, socioeconomic factors and other considerations that may arise which are connected to EDI.

Internal pilot study

Prior to embarking on the efficacy study an internal pilot study will be undertaken. The aim of the internal pilot study is to explore whether it is feasible to deliver MDFT in the UK context and establish key parameters to incorporate into the design of the efficacy study. Progression criteria are detailed in appendix II and the study will be conducted between September 2025 with a transition decision in June 2026.

In the pilot study we will recruit 60 participants, 30 in each arm, across the 2 sites. This will allow for exploration of key parameters needed to confirm sample size calculation for the efficacy study. It is sufficient to allow estimation of two-sided 95% CIs around the proportions of eligible, consenting, adhering and followed up at month 6 in each arm of the study with half-widths less than 0.15. It meets the 30 per group recommended by Lancaster et al (Lancaster et al., 2004) for estimating the SE of a primary outcome with sufficient precision, including accounting for any variation across site, where 12 participants per arm per site is recommended.

Objectives for the internal pilot trial

- **PRQ1** To conduct a prospective, two-arm, individually randomised RCT to pilot study outcomes and methods and establish the parameters for the conduct of efficacy evaluation.
- **PRQ2** To assess whether progression criteria have been met and develop an appropriately powered efficacy protocol.
- **PRQ3** To confirm the pre- post-test correlation on the primary outcome, percent days abstinent from alcohol and/or drugs to incorporate into a sample size calculation.
- **PRQ4** To estimate an estimate of potential effect for the primary outcome for inclusion in a sample size calculation.
- PRQ5 To explore the relationship between the use of alcohol and specific drugs and violent offending. This will be achieved through an analysis of existing datasets; Reframe and RISKIT-CJS, with a confirmatory analysis conducted on the pilot data at the time of transition.

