- **PRQ6** To explore data redundancy at the 6-month end point to provide information on outcome assessments.
- PRQ7 To explore what constitutes business as usual across the two sites, Bristol and Newport.
- **PRQ8** To qualitatively explore the feasibility, acceptability and barriers associated with referral pathways with a particular focus on equity, diversity and inclusion.
- **PRQ9** To qualitatively explore intervention delivery and outcome assessments from the perspectives of participants, their family, intervention providers and key stakeholders.
- **PRQ10** To explore the cultural sensitivity of the intervention and trial methods and explore whether further adaption to the intervention is necessary.
- **PRQ11** To explore whether MDFT has any iatrogenic or unintended consequences.

Design

The study protocol has undergone an independent equality impact assessment (EIA) (appendix III). The EIA explores equity, diversity, and inclusion from a variety of perspectives. The EIA was coproduced with a Young Persons Advisory Group (YPAG). The MDFT intervention will undergo an initial adaption stage, coproduced with an advisory group who are representative of the population where the intervention will be delivered.

Information sheets, privacy notices and consent forms are designed to be understood and completed by young people. All outcome measures are validated for the age of the target population. Experts in the design of research for young people with intellectual disabilities, SEND and neurodiversity will be consulted to ensure the materials align with best practice. Where necessary translated materials will be prepared to meet the needs of a diverse ethnic population and where translated versions are not available, translators, including British Sign Language will be made available. Initial assessment will be conducted in a variety of Barnardo's and community locations that are accessible irrespective of disability status and young people will be encouraged to choose a location they find most comfortable. Follow-up assessments will be conducted using a video link and conducted by a researcher with experience of working with marginalised young people.

The recruitment of MDFT therapists will be conducted through local organisations and aim to reflect the diversity of the population where it will be delivered. Young people will be able to choose a therapist who their own cultural or ethnic background or protected characteristics.

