Targeting those at the greatest risk of serious youth violence will be a key priority. The prioritisation of referrals will be decided using a multi-agency approach via intelligence sharing between Barnardo's, Local Authority and education safeguarding teams and Police across Bristol and Newport. It is expected that 70% of referrals will be secondary, not currently involved with CJS and 30% tertiary, currently involved with CJS. Referrals will come from services in Bristol and Newport who are in contact with vulnerable children with known or suspected substance use problems, including schools, Pupil Referral Units, Youth Offending Services, Children's Social Services, CAMHS and specialist drug and alcohol services. It is anticipated that most referrals will come through an agreed referral pathway with both Local Authorities (LA), of their Front Door arrangements, Youth Justice Teams and Violence Reduction / MACE arrangements. Following discussions with both LAs, Barnardo's is

confident that sufficient referrals will come from this pathway to meet the required numbers. In addition, referrals may also be made by other services. This is a similar approach to that adopted by Barnardo's Strategic Child Exploitation Service in Bristol which works directly with young people at the highest risk of harm - gang involvement, serious violence, and exploitation. Initial estimates suggest 35% of participants will be from Black, Asian or other racially minoritised groups, 35% will have special educational needs or disabilities, 15% will be care experienced and 35% female.

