We will ensure participants do not feel coerced to consent. Once a participant is referred to the service any consent to participate in the trial is theirs solely to make. Not consenting to the research will not impact on the BAU they receive, and this will be explained verbally and in writing. If a participant does consent it will be made clear that they can withdraw consent at any time.

We will minimise the potential for participants and staff to experience any adverse or iatrogenic events. In our experience of conducting similar studies in similar populations the risk of adverse events is low, as is the risk of iatrogenic events. We will implement a standard operating procedure for the reporting of adverse events that involves an independent

experienced third-party making recommendations on the severity of any event and whether they are associated with the trial. All staff involved in the study will have enhanced DBS accreditation and will be familiarised with safeguarding practice and procedures.

University of Kent Social Research Ethics Identifier: SRE 1200

Barnardo's Research Ethics Committee Identifier: BREC (23)

Trial Registration: ISRCTN10024151

Data protection

All systems and personnel are approved for the management of clinical and sensitive data and are ISO certified to ISO27001 standard. This includes all physical systems, systems to detect intrusion, encryption of data from point of collection to storage, quality assurance and audit trails associated with any data collected. All identifiable data collected will be done with explicit consent and limited to data to allow participants to be contacted for follow-up. Data linkage will employ a unique identifier where the link to identifiable information will be stored on an encrypted secure database. Researchers will be trained to GCP standard and will comply with all relevant data protection legislation. Once final follow-up is completed, personally identifiable information will be deleted from the dataset held by the university and where consent to the trial has been granted encrypted data will be transferred to the Youth Endowment Fund data archive. Consent for transfer of data will be taken from those resident in England, and data used by DfE, name, DoB and postcode will be transferred. Data collection and management will be governed by a trial specific Standard Operating Procedure agreed and approved by ethics.

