Young people may not want to consent to being part of study resulting in lack of numbers for the evaluation	Young people will have access to a clear information sheet highlighting the need to evaluate a new service. Information will be reviewed by a young person's advisory group who will provide input on how best to engage young people in the research. Our experience of other studies with similar populations is that many young people are motivated by altruism, the opportunity to contribute to services that will help others in a similar position in the future.

The potential that young people, therapists and researchers experience negative impacts of participating in the study.	All staff and researchers have access to supervision to raise issues relating to the trial. We will implement a reporting system to allow all staff, young people and their carers and researchers to highlight any potential adverse events and, if needed, seek support. We will implement an independent DMEC to review adverse and iatrogenic effects as they arise and if they believe these are directly attributable to the trial and severe in nature, they will raise the potential of stopping the trial with the research team and funder.
Families may be resistant to participating in the trial.	We have extensive experience of including marginalised populations in evaluations. The pilot study will explore qualitatively barriers to participation. All information about the trial will be available in advance of consent and potential participants provided an opportunity to discuss participation. Consent will be based on the consent of the young person rather than the family and early work in delivering MDFT identifies the most appropriate family members to be involved in the delivery of MDFT.
Young people may exhibit demoralisation if randomised to BAU rather than the MDFT intervention.	Clear information to participants that the study involves a state of equipoise, that at this stage we have no evidence that MDFT is better than BAU and this is what is being tested. Disengagement and 'faking bad' are key signs of resentful demoralisation and both concepts will be explored qualitatively with young people.

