Appendix II: Progression criteria from internal pilot

Project implementation

Area	Question	Assessment	Criteria	Rag rating
Therapist Recruitment	Have sufficient therapists been	Number of therapists recruited	7	>6 in post
	recruited			<6 >4 in post
				<4 in post
Therapist Training	Have sufficient therapists been	% of therapists certified	75%	>75%
	certified			60 – 74%
				<60%
Therapist Supervision	Do therapists attend planned supervision	% of therapist supervision sessions attended	75%	>75%
				60 – 74%
				<60%
Therapist Capacity	ls there sufficient capacity to provide MDFT Is there sufficient capacity to provide capacity Model of randomisation/ capacity		100%	100%
			90-99% increase number of therapists by 1	
				<90% increase number of therapists by required number
			80%	>80%

Dosage within 4-6 months 55% adolescent sessions 30% family sessions 15% parent alone sessions	Do participants comply with the minimal dose of MDFT	% participants receiving minimal dose		60-79% <60%
Eligible referrals	Are sufficient referrals eligible	% of eligible participants who consent	80%	>80% 50 - 79% <50%
Acceptability of adaptions	Are the adaptions to MDFT acceptable to therapists and participants	Review of adaptions	Adaption should be acceptable	Acceptable to some but not all revise adaption Not acceptable

Internal pilot evaluation

Area	Question	Assessment	Criteria	Rag rating
Participant recruitment	· ·	60	60	
				42-60
				<42
Evaluation attrition	aluation attrition Have sufficient % of participan participants been retained		90%	>90%
				70 – 89%

	retained at 6- months			<70%
Proportion with primary outcome	Have sufficient participants	% of participants completing primary	95%	>94%
recorded at month	provided a primary outcome	outcome		75 – 94%
				<75%%
Proportion with secondary outcome	Have sufficient participants	% of participants completing	80%	>80%
recorded at month 6	provided a secondary	secondary outcome		60 – 79%
	outcome			<60%
Analysable primary and secondary	secondary participants who providing usefull	providing usefull primary and secondary	80%	>80%
outcome data				60 – 79%
		outcomes		<60%
Randomisation	Are the groups allocated to MSFT and BAU of similar size	Difference in the proportion allocated to each group	2%	<2%
				3-5%
				>5%
Randomisation	Are the groups allocated to MSFT	Difference in the proportion allocated to each group by	5%	<5%
	and BAU of similar size by stratification			5-10%
stratific		stratification		>10%

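### The stated stopping trigger rests on attribution and severity, no review of harm by arm is specified, and the pilot progression criteria have no harm row although PRQ11 makes harm a pilot objective

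*Protocol*

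**What the plan says.** **Stopping.** In the Protocol's Risks table, the row on negative impacts of taking part says: "We will implement an independent DMEC to review adverse and iatrogenic effects as they arise". It continues: "if they believe these are directly attributable to the trial and severe in nature, they will raise the potential of stopping the trial". The DMEC's step is advisory, since it raises the matter with the research team and funder.

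**Event assessment.** The Ethics and registration section describes a standard operating procedure with an independent "experienced third-party making recommendations on the severity of any event and whether they are associated with the trial". It states from earlier experience that "the risk of adverse events is low, as is the risk of iatrogenic events", without giving a figure.

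**Pilot objective.** PRQ11, under Objectives for the internal pilot trial, is "To explore whether MDFT has any iatrogenic or unintended consequences".

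**Pilot gate.** The Internal pilot study section says "Progression criteria are detailed in appendix II". Appendix II rates therapist recruitment, certification, supervision and capacity; dose; consent among eligible referrals; acceptability of the adaptations; recruitment; attrition; completeness of outcome data; and allocation balance.

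**Pilot analysis.** The Pilot study analysis section plans descriptive statistics for each outcome measure, including by allocated group, and a futility analysis of the primary outcome whose stated use is to confirm or revise the sample size.

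**Population.** The Participants section says "Targeting those at the greatest risk of serious youth violence will be a key priority" and expects 30% of referrals to be currently involved with the criminal justice system. The background section cites a mental health need in 72% of young people in that system.

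**The concern.** The harms that a family-based psychosocial intervention could plausibly cause are more offending, violence, conflict at home, substance use or distress. They are also what many of these young people will experience whichever arm they are in. An assessor looking at one arrest or assault will seldom be able to say that the trial directly caused it. Where cause cannot be judged case by case, the evidence a randomised trial can offer is an excess over the comparator, and the stated trigger does not refer to that.

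The second decision point is the June 2026 transition, and it does not fill the gap. Harm is a named pilot objective, but nothing in Appendix II turns the answer into a decision. On the Timeline, 340 further adolescents are recruited after that point.

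**Working it through.** No harm rate, harm threshold or stopping boundary is stated, so there is no figure to reproduce. The check is mainly a comparison of texts, followed by an illustration on assumed rates.

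**1. The trigger.** The Risks table wording joins two conditions: directly attributable to the trial, and severe. Suppose events occur more often under MDFT but each looks like a background event. Assessed event by event, the first condition fails for each, and the trigger as written is not met. The visible text specifies no review by arm, review interval or pause step.

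**2. The pilot gate.** Set PRQ11 beside the other pilot text:

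- Pilot study analysis tags its work to PRQ1 to PRQ9. PRQ10 (cultural sensitivity) is untagged but its content is described. PRQ11 has neither a tag nor described content there.
- Interviews on unintended consequences appear in the section on adapting MDFT, and cover MDFT recipients and the therapists.
- No Appendix II row concerns adverse events or worsening. More violence or arrests under MDFT would leave every rating unchanged.

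**3. What will exist at transition.** On the Timeline the pilot recruits from 09/25 to 12/25. Adding 6 months puts its follow-up at 03/26 to 06/26. Table 4 lists SRDS, SDQ, SWEMWBS, BFRS and CSRI at baseline and six months. The by-arm tables needed for a harm judgement are therefore already planned, but nothing links them to the decision.

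**4. Could a formal test at the pilot do the job?** Two-sided alpha 0.05, n per arm, assumed event proportions p1 and p2 with mean p̄:

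power = Φ( [ |p1 − p2| − 1.96·√(2p̄(1 − p̄)/n) ] / √( [p1(1 − p1) + p2(1 − p2)]/n ) )

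For 10% against 20%, p̄ = 0.15:

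- n = 30: (0.10 − 1.96 × 0.0922)/0.0913 = −0.88, so power is 19%.
- n = 200: (0.10 − 1.96 × 0.0357)/0.0354 = 0.85, so power is 80%.

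| Assumed rates | 30 per arm | 200 per arm |
|---|---|---|
| 2% vs 4% | 7% | 22% |
| 5% vs 10% | 11% | 48% |
| 10% vs 20% | 19% | 80% |
| 10% vs 30% | 49% | over 99% |

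Nor is an absence of events reassuring: 0 of 30 leaves a one-sided 95% upper limit of 1 − 0.05^(1/30) = 9.5%. A pilot significance test would rarely detect a doubling. Accumulating by-arm data could, if the base rate is not very low.

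**The case against.** **The wording is broader than a rule about one event.** The text speaks of effects in the plural, so a DMEC could treat an accumulated imbalance as an attributable effect. Event-level assessment belongs to a different body, the third party in the Ethics section. This stands. A reader might infer that one severe, attributable event is required; the text does not say so.

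**Nothing forbids other action.** A mitigation cell in a risk table says when the DMEC will raise stopping. It does not bar by-arm data or advice on other grounds. Meeting schedules and closed tables often sit in a charter or safety procedure, and neither is at hand; a stretch of text before the visible part of the risk table was also not available to check. This stands against any claim that the trial cannot be stopped or paused for an excess of harm. It does not alter the fact that the protocol itself states a narrow trigger and an incomplete gate.

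**The comparator is measured.** Outcomes are tabulated by allocated group, and the futility look would show worse substance use under MDFT. This stands, so it would be wrong to say that PRQ11 cannot be answered. What is missing is an assigned analysis and a consequence.

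**Scale data arrive late.** Efficacy six-month follow-up runs from 01/27 to 11/27, while recruitment ends in 05/27 and delivery in July 2027. This stands in part. During efficacy recruitment, review will lean on adverse events, pilot data and the earliest efficacy follow-ups, which makes the June 2026 review more important.

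**A DMEC-judged row largely repeats continuing DMEC review.** Only if that review looks at harm by arm, which is not stated.

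**Conclusion.** The point holds in a limited form and should be acted on before transition. The only stated route to stopping depends on attribution and severity together, no cumulative by-arm review of harm is specified, and a named pilot objective on harm has no counterpart in the progression criteria. Followed as written, the pilot can be green on every row with more violence or arrests under MDFT.

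The stronger conclusion, that harm in one arm is bound to go unseen or that the DMEC is powerless, is not supported: by-arm data will exist and no text restricts the DMEC's advice.

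The practical size depends on event rates that the protocol does not give. The powers above rest on assumed rates of 2% to 10% doubling, with one case tripling, and serve only to show that the pilot step should be a judgement and not a test. The count of 340 adolescents recruited after transition follows the Timeline; the sample size section instead describes recruitment as continuous from September 2025, in which case more than 60 could already be enrolled by then.

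**What to change.** **Appendix II.** Add a harm row that answers PRQ11, rated by the DMEC at the June 2026 transition. Green: no concern after by-arm review. Amber: continue with stated changes. Red: the DMEC recommends stopping. The material is adverse events by arm plus the tables already planned: SRDS violent volume, CSRI arrests and charges, BFRS conflict, SDQ and SWEMWBS. State that the rating is a judgement and not a significance test.

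**Risks table, and the DMEC charter if there is one.** State that the DMEC also reviews cumulative by-arm adverse events and these outcome data at set intervals during efficacy recruitment. State that it may raise pausing or stopping on an imbalance between arms, as well as on effects judged attributable and severe.

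**Cost.** A row, a sentence or two, and a few closed tables. No new data collection and no change to sample size. The one real burden is that someone outside the blinded team must prepare the closed report, because follow-up and the efficacy analysis are meant to be blind to allocation.

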Appendix I: Theory of Change Narrative

Preconditions

Practitioners with a level 4 or equivalent qualification in psychology, social work, youth work, nursing or occupational therapy, post-graduate qualification, or equivalent, in therapeutic interventions. Experience in working with young people in a therapeutic environment. Staff are recruited and managed by Barnardo's who provide access to safe and supportive therapeutic spaces both those owned by Barnardo's and those accessed through existing community partnerships. Staff are managed by senior staff embedded within the proposed sites, Bristol and Newport.

Population need

Most adults with problematic substance use report that their substance use began in adolescence (Simon et al., 2022). Young people are much more vulnerable than adults to the adverse effects of substance use due to a range of physical and psychological factors that often interact and the differential impact of substances on the developing brain (Battistella et al., 2014, Copeland et al., 2013b, Parlar et al., 2021). In addition to an increased risk of accidents and injury (NHS., 2018), substance use in adolescence is also associated with poor educational performance and exclusion from education. Over the academic year 2015-16, almost 9% of permanent school exclusions in state secondary schools were due to alcohol and substance use (DFE., 2019).

While the relationship between offending behaviour and substance use is complex, evidence highlights that the prevalence of substance use is far higher in the youth offending population than the general youth population. Approximately 25% of young people in structured alcohol and drug treatment are referred from criminal justice (OHID., 2022) and data from the Youth Offending Team, ASSETPLUS, indicates that 76% of young people in the CJS use alcohol and other illicit substances.

There are few well-evidenced substance misuse programmes being delivered in England and Wales. In the areas targeted, Bristol and Newport, the treatment as usual consists of a combination of motivational interviewing and/ or motivational enhancement therapy, both interventions that focus on a single domain, substance use, with limited evidence of sustained effectiveness and no evidence of effectiveness in reducing offending.

Multidimensional family therapy (MDFT) is an integrative, family-based, multiple systems-oriented treatment specifically targeted at adolescent substance users (Liddle and Schwartz, 2002). The case for evaluating MDFT here is founded on:

• Strength of existing evidence and likely impact - MDFT is one of the most robustly evidenced substance misuse interventions globally, with several RCTs across the USA and Europe (Dakof et al., 2015, van der Pol et al., 2017a), and strong evidence ratings by the Early Intervention Foundation and several research clearing houses in the US. Unusually for a youth violence intervention it has been the subject of systematic review which concluded MDFT reduces drug use severity 6 months post-test, when compared to other treatments such as CBT (Dakof et al., 2015, van der Pol et al., 2017a). MDFT has been found to reduce rates of cannabis dependence and externalising behaviours

in a trial across Belgium, France, Germany, The Netherlands and Switzerland (Rigter et al., 2013). Collectively these studies establish MDFT as a promising programme that has shown impact in countries like the UK.

- Robust evidence of reducing offending In the USA MDFT has demonstrated an impact on number of arrests 18 months after the intervention was delivered (Liddle et al., 2024a).
- Ability to get to trial MDFT has undergone multiple evaluations in a range of geographies and delivery settings and developers show a strong commitment to robustly evaluating the programme in the UK.

Given the strength of evidence across a range of outcomes - as well as long-term impact on offending and the developers' commitment to evaluation, there is a strong case to trial this programme in the UK. Given the range of outcomes, it seeks to address, if effective, the impact of MDFT could extend beyond youth violence and be a part of government efforts to improve outcomes for vulnerable children, including through the Family Hubs initiative and the response to the Care Review.

In addition, there is strong demand in Bristol. A recent scrutiny report shows that Bristol has experienced an increase in the number of young people referred for services relating to extra-familial harm (up 18.3%) and an increase in child vulnerability due to poverty and inequality. The Children's Commissioner for England estimates that in 2019/20 there were 4,600 children and young people aged 0-17 living in households in Bristol with a parent who has alcohol or drug dependence. In Wales, substance misuse among children and young people represents a particular societal focus — figures from March 2022 for Newport show above average levels of substance misuse identified as a concern for YP receiving support and care: 10% (Wales average 7%) had their own substance misuse as a primary concern and 33% (Wales average 31%) had parental substance misuse as a primary concern.

Population

Inclusion criteria:

- 1. Young people aged 13-17 years inclusive.
- 2. Currently involved with the police or youth justice service or at risk of offending.

At risk of offending defined as having at least one of the following risk factors, assessed on referral.

Previously being in the secure estate.

Currently, or previously, persistently absent from school (defined by DfE as 10% or more). Have been the victim of violence.

Currently, or have attended alternative education provision.

Received multiple suspensions from school or has been permanently excluded.

Have a sibling or parent who has been involved in serious violence or identified as facing exploitation harm.

Currently, or have been, in the care system.

Have been identified as being at risk of criminal exploitation.

Currently or have had a social worker.

Have previously been in contact with youth justice services.

Have been arrested, admitted an offence and released by the police with no further action.

- 3. Evidence of alcohol or substance use on at least 4 occasions in the past 28 days, assessed using a single substance use frequency question.
- 4. Willing and able to provide informed consent or willing to provide assent with a parent/ carer willing to provide consent.

Exclusion criteria:

- Alcohol or substance severity that requires inpatient residential treatment or immediate detoxification.
- 2. Severe mental health condition requiring immediate psychiatric assessment.

Inputs

In both sites, as a Strategic Partner for both LAs, Barnardo's has the local relationships to ensure effective referral pathways are put in place. It has been agreed that referrals will primarily come through the Front Door of each LA as well as through both Youth Justice Teams. In Bristol, the new MACE (Multi-Agency Child Exploitation) arrangement, which has oversight of young people at risk and those being harmed through exploitation, will also act as a key referrer.

MDFT will be adapted for delivery in the UK context. Adaption follows the ADAPT guidance (Moore et al., 2021) to ensure the intervention that aims to maximise the efficacy by ensuring they fit well within a UK delivery context.

Staff recruitment will recruit a broad, culturally diverse range of therapists by advertising roles in community venues and within local community networks. Barnardo's training offer for all staff supports culturally sensitive delivery. Where possible, consideration will be given to matching the young person and therapist. This might be along lines of shared protected characteristics, interests and when the therapist has a particular skill set that will meet the young person's needs. As part of induction, all staff undertake an equality, diversity and inclusion course, which includes discussions around culturally sensitive delivery, unconscious bias and understanding the experience of children from different backgrounds. Learning and Development is supported by SEEN (https://weareseen.org.uk/), the national resource centre to improve outcomes for children and young people of African, Asian and Caribbean heritage. As part of the support offered to all staff through SEEN, there is a knowledge bank containing resources such as: 'An emancipatory approach to cultural competency: The application of critical race, postcolonial, and intersectionality theories', 'Anti-racist supervision (for professionals)' and 'Being Black in rural spaces (UK Youth)'.

Therapists need access to safe, supportive and therapeutic spaces within the community in which they can build relationships with children and families. Barnardo's has access to community buildings through partnerships with the Local Authorities, VCSE networks and youth work providers across Newport and Bristol. Local management are embedded within both Newport and Bristol, and are fully cognisant of local factors including geography, demography, need and support services, allowing us to target and understand the background and support needs of children and families, and access resources as required.

In Bristol, Barnardo's own a building at Old Market (Bristol Centre), which is located for ease of access to children and families. It has been decorated in co-production with young people who use it to be welcoming, therapeutic and trauma-informed throughout, and contains dedicated safe spaces for therapeutic delivery.

The MDFT team in each site usually consists of 6-8 therapists, one who is trained to act in a supervisory role. Training in MDFT is provided by MDFT international who provide an intensive training package and full certification. Training includes the assessment of the needs of children and families and case formulation to meet those needs. All therapists have access to supervisory support from the site based MDFT supervisor and the wider MDFT international team. MDFT therapists have access to the MDFT portal to record planned and delivered sessions.

Activities

The specification with respect to number of adolescent alone session, parent sessions without their adolescent, family sessions are guidelines are not dictates or requirements. The exact configuration is very individualised to the need of the young person and family. MDFT is not a curriculum-based intervention but instead is a psychotherapy where the exact interventions applied, types of sessions, weekly dose, length of treatment episode is determined by the needs of the young person and family. A minimum dosage is considered 12 sessions over a 4-month period.

MDFT typically consists of 2 sessions per week lasting anywhere from 45 to 90 minutes. 90 minutes may be necessary for multipart family sessions. Individual sessions alone with the young person typically range from 45 – 60 minutes, sessions alone with the parents are usually 60 minutes.

Mechanisms

A key aspect of MDFT involves building a strong therapeutic alliance with young people and their parents/ carers as the foundation of achieving behaviour change. Therapeutic alliance is assessed using the Therapeutic Alliance Scale for Children (TASC-r; (Shirk and Saiz, 1992). Where young people feel included in decision making and experience a sense of positive collaboration with the therapist and families experience consistency in the support

Young people develop an enhanced motivation to change their substance using behaviour, assessed using the readiness ruler (RR; (Maisto et al., 2011). They develop better strategies for managing situations where they would previously engage in substance use, assessed using the situational confidence questionnaire (SCQ; (Breslin et al., 1998) and they have a better understanding of their own strengths and a greater appreciation of the negative aspects of substance use, assessed using the substance use expectancy measure (SUE; (Montes et al., 2019). Families experience greater communication, less conflict and are empowered to solve problems

collaboratively, assessed using the brief family relationship scale (BFRS; (Fok et al., 2014)).

In the study the influence of these mechanisms on substance use and offending will be explored using a latent class mediation model approach that aims to identify implicit subgroups among the study population based on their response to a set of process (mechanistic) variables hypothesised to influence change. These variables are assessed at baseline, prior to randomisation and again at 6-months post-randomisation.

Short term outcomes

Short term outcomes are measured at baseline and again at 6-months post-randomisation.

Changes in the frequency, quantity and type of substances is assessed using the time line follow-back method over a 28-day retrospective period (TLFB 28; (Sobell and Sobell, 1995). Violent, non-violent and antisocial behaviour is assessed using the self-report delinquency scale (SRDS; (McAra and McVie, 2007). Emotional regulation, internalising, externalising and prosocial behaviours, and conduct issues are assessed using the strengths and difficulties questionnaire (SDQ; (Goodman, 1997)). Wellbeing and mental health are assessed using the Warwick Edinburgh mental wellbeing scale (WEMWBS; (Clarke et al., 2011)). The frequency of school attendance, exclusion, suspensions and involvement with the police and criminal justice system is assessed using a short form client service receipt inventory validated in other studies of adolescent substance using populations (CSRI; (Coulton S et al., 2023, Coulton et al., 2024)). Substance use related problems are assessed using the European School Project on Alcohol and Drugs problem domain (ESPAD; (Group, 2021).

Long term outcomes

Long term outcomes occur beyond the horizon of the trial. They are considered as longer-term impacts associated with changes observed in the short-term outcomes. Sustained reductions in substance use. Greatly reduced violent and non-violent offending due to reductions in risk factors associated with offending behaviour and fewer externalising and conduct behaviours. Improved educational attainment due to reduced absenteeism and less disengagement with education leading to increased propensity to remain in education or transition to employment. Improved physical and psychological health due to reduced substance use and fewer internalising behaviours and a more positive transition to adulthood.

